10.3.4 Reporting of SAE

Investigator Reporting Responsibilities

Any SAE must be reported to the sponsor on the (paper) SAE form immediately, without undue delay but not later than within 24 hours of obtaining knowledge. This report should contain among others an assessment of available information on seriousness, severity, causal relationship to the IMP or trial procedure, the action taken, the outcome to date, and a narrative description of the course of the event. For more details regarding reporting of any SAE, please see the guidance text on the SAE form.

By signing and dating the SAE form, the investigator acknowledges that he/she is aware of the SAE and has assessed the causal relationship of the IMP(s) and any of the other medications to the SAE.

The actual reporter, if not the investigator, should also sign and date the SAE form.

The completed SAE form must be faxed or scanned and e-mailed to Global Safety at LEO Pharma using the e-mail address or fax number below:

Global Safety at LEO Pharma

E-mail address: [contact]

[contact]

If relevant, the investigator will enclose other information with the SAE form, such as anonymised reports of diagnostic procedures, hospital records, autopsy reports, etc.

Additionally, Global Safety at LEO Pharma may request further information in order to fully assess the SAE. The investigator must forward such information to LEO Pharma upon request by fax or e-mail (see contact details above).

The investigator must notify the local IRB(s)/IEC(s) of SAEs, as required by current applicable legislation for the concerned country.

SAEs occurring after the completion of the clinical trial should not be routinely sought or recorded. However, such events should be reported to Global Safety at LEO Pharma (see contact details above) if the investigator becomes aware of them.

Sponsor Reporting Responsibilities

Global Safety at LEO Pharma is responsible for assessing whether an SAE is expected. The relevant reference safety information documents for this clinical trial are:

- For delgocitinib, the IB Section 7.3 for delgocitinib cream, edition 5.0 (Delgocitinib cream IB, 2022) and subsequent updates must be used.
- For alitretinoin (Toctino[®]), the latest version of the SmPC must be used (Toctino[®] SmPC, UK).

Global Safety at LEO Pharma will notify the regulatory authorities and concerned investigators of SAEs according to the current applicable legislation for the concerned countries.

The IRB(s)/IEC(s) will be notified of SAEs according to the current applicable legislation for the concerned countries.

The following reporting requirements apply: all SAEs which are assessed as causally related to the IMP(s) by either the investigator or the sponsor, and which are unexpected (i.e. suspected unexpected serious adverse reactions [SUSARs]), are subject to expedited reporting to regulatory authorities, and IEC(s)/IRB(s) according to the current applicable legislation in the concerned countries. Investigators will be notified of the evolving safety profile of the IMP on an ongoing basis.

10.4 Appendix 4: Contraceptive and Barrier Guidance

10.4.1 Definitions

Woman of Childbearing Potential (WOCBP)

Women in the following categories are considered WOCBP (fertile):

- 1. Following menarche
- 2. From the time of menarche until becoming postmenopausal unless permanently sterile (see below)
 - A postmenopausal state is defined as no menses for 24 months without an alternative medical cause.
 - A high follicle-stimulating hormone (FSH) level in the postmenopausal range may be used to confirm a postmenopausal state in women not using hormonal contraception or hormonal replacement therapy (HRT). However, in the absence of 24 months of amenorrhea, confirmation with more than 1 FSH measurement is required.
 - Females on HRT and whose menopausal status is in doubt will be required to use 1 of the non-oestrogen hormonal highly effective contraception methods if they wish to continue their HRT during the trial. Otherwise, they must discontinue HRT to allow confirmation of postmenopausal status before randomisation.
 - Permanent sterilisation methods (for the purpose of this trial) include:
 - Documented hysterectomy
 - o Documented bilateral salpingectomy
 - o Documented bilateral oophorectomy
 - For individuals with permanent infertility due to an alternate medical cause other than the above, (e.g. Mullerian agenesis, androgen insensitivity, gonadal dysgenesis), investigator discretion should be applied to determining trial entry.

Note: Documentation can come from the site personnel's review of the participant's medical records, medical examination, or medical history interview.

• If fertility is unclear (e.g. amenorrhea in adolescents or athletes) and a menstrual cycle cannot be confirmed before first dose of trial treatment, additional evaluation should be considered.

Woman of Nonchildbearing Potential (WONCBP)

Women in the following categories are considered WONCBP:

- 1. Premenopausal woman with permanent infertility due to 1 of the following:
 - a. Documented hysterectomy

- b. Documented bilateral salpingectomy
- c. Documented bilateral oophorectomy
- d. For individuals with permanent infertility due to an alternate medical cause other than the above, (e.g. Mullerian agenesis, androgen insensitivity, gonadal dysgenesis), investigator discretion should be applied to determining trial entry.

Note: Documentation can come from the site personnel's review of the participant's medical records, medical examination, or medical history interview.

2. Postmenopausal woman

- a. A postmenopausal state is defined as no menses for 24 months without an alternative medical cause.
 - A high FSH level in the postmenopausal range may be used to confirm a
 postmenopausal state in women not using hormonal contraception or HRT.
 However, in the absence of 24 months of amenorrhea, confirmation with more
 than 1 FSH measurement is required.
 - ii. Women on HRT and whose menopausal status is in doubt must discontinue HRT to allow confirmation of postmenopausal status before randomisation.

10.4.2 Contraception Guidance

Women of childbearing potential must use at least one highly reliable method of contraception (i.e., a user-independent method) or two complementary user-dependent methods of contraception. Contraception must be used 1 month before treatment and throughout the treatment period, including participants with amenorrhea. Contraception must additionally be used for 1 month after the end of treatment with alitretinoin. If local guidelines have stricter requirements, then local guidelines should be followed.

CONTRACEPTIVES ^a ALLOWED DURING THE TRIAL INCLUDE:

Highly Effective Methods^b That Have Low User Dependency

Failure rate of < 1% per year when used consistently and correctly.

Implantable progestogen-only hormone contraception associated with inhibition of ovulation^c.

Intrauterine device (IUD).

Intrauterine hormone-releasing system (IUS)^c.

Bilateral tubal occlusion.

Azoospermic partner (vasectomised or due to a to medical cause)

Azoospermia is a highly effective contraceptive method provided that the partner is the sole sexual partner of the WOCBP and the absence of sperm has been confirmed. If not, an additional highly effective method of contraception should be used. Spermatogenesis cycle is approximately 90 days.

Note: documentation of azoospermia for a male participant can come from the site personnel's review of the participant's medical records, medical examination, or medical history interview.

Highly Effective Methods^b That Are User Dependent

Failure rate of <1% per year when used consistently and correctly.

Combined (oestrogen- and progestogen-containing) hormonal contraception associated with inhibition of ovulation^c

oral

intravaginal

transdermal

injectable

Progestogen-only hormone contraception associated with inhibition of ovulation^c

oral

injectable

Sexual abstinence

Sexual abstinence is considered a highly effective method only if defined as refraining from heterosexual intercourse during the entire period of risk associated with the IMP. The reliability of sexual abstinence needs to be evaluated in relation to the duration of the trial and the preferred and usual lifestyle of the participant)

- a) Contraceptive use by men or women should be consistent with local regulations regarding the use of contraceptive methods for those participating in clinical studies.
- b) Failure rate of < 1% per year when used consistently and correctly. Typical use failure rates differ from those when used consistently and correctly.
- c) Male condoms must be used in addition to hormonal contraception. If locally required, in accordance with Clinical Trial Facilitation Group guidelines, acceptable contraceptive methods are limited to those which inhibit ovulation as the primary mode of action.

Note: Periodic abstinence (e.g. calendar, symptothermal, post-ovulation methods), withdrawal (coitus interruptus), spermicides only, and lactational amenorrhoea method are not acceptable methods of contraception. Male condom and female condom should not be used together (due to risk of failure with friction).

10.5 Appendix 5: COVID-19 Pandemic Contingency Plan

Without compromising the safety of participants and trial integrity, it is expected that efforts are made to secure attendance at sites for all visits, ensuring important efficacy and safety assessments for the trial

If on-site visits are not possible due to local authority-issued preventive measures, the affected site will postpone screening and randomisation of new participants until on-site visits can be conducted. For already randomised participants, post-baseline visits can be done remotely via phone or video. At phone/video visits, no investigator assessments of efficacy can be done, but the following data will be collected remotely, according to the SoA (Table 1-1):

- AE reporting.
- Treatment compliance (daily completion in the eDiary).
- Concomitant medication and concurrent procedures.
- HESD (daily completion in the eDiary).
- Participant assessment of local tolerability (weekly completion in the eDiary).
- PROs (DLQI, HEIS, EQ-5D-5L, TSQM, WPAI-CHE, PGI-S, and PGI-C). The participants will receive a link to complete the PROs in a web browser from their own device.
- New CHE lesions.
- Urine pregnancy test. Women of childbearing potential will receive 1 extra urine pregnancy test at the randomisation visit to keep at home in case on-site visits become impossible during the trial. The participant will perform the test at home and inform the investigator about the result via phone and to send a picture of the test to the site or show it via video. Additional urine pregnancy tests can be shipped to the participant's home together with IMP (see below) if needed.
- For participants treated with alitretinoin:
 - Serum cholesterol and serum triglycerides (fasting values) should continue to be monitored by a local laboratory, at the timepoints outlined in the SoA (Table 1-1).
 - Remote consultation to allow for adequate monitoring of mental health should be maintained at the timepoints outlined in the SoA (Table 1-1). The potential for psychiatric disorders may be increased by COVID-19 isolation measures and this may complicate the clinical picture.

In the eCRF, it will be recorded whether a visit or a given assessment was done remotely or not done. If not done, it will be recorded if this was due to the COVID-19 pandemic.

It will be at the discretion of the investigator to decide whether clinical laboratory samples are considered necessary to ensure participant safety in periods when on-site visits are not possible. If possible, a home visit can be arranged for a healthcare professional to collect relevant clinical laboratory samples.

Contingency plans due to COVID-19 must follow the authorities' COVID-19 guidelines and local requirements. Written procedures describing the contingency plan must be in place at site and depot. To ensure availability of IMP, the trial sites will dispense additional IMP if considered relevant (i.e. if local authority-issued preventive measures are to be expected at the given trial site). This will allow participants to continue IMP although they are not able to go to the trial site. If a participant will not be able to attend on-site visits due to the COVID-19 pandemic before running out of IMP, the trial site will ensure shipping of IMP to the participant's home. As the participants' IMP supply is secured, the IE of initiation of rescue treatment will be considered independent of the COVID-19 pandemic in the statistical analysis.

If a participant is tested positive for COVID-19, the investigator will evaluate whether this is an AE that contraindicates further dosing, in which case the participant will permanently discontinue IMP as described in Section 7.1.

10.6 Appendix 6: Liver Safety: Suggested Actions and Follow-up Assessments10.6.1 Liver Chemistry Monitoring and Reporting

In case of an increase of ALT and/or AST ≥5×ULN, re-sampling for ALP, ALT, AST, bilirubin, and prothrombin INR should be done immediately, without undue delay and no later than within 72 hours from initial sampling time to confirm abnormalities. Re-sampling may be relevant at lower levels at the discretion of the investigator. Participant should be monitored weekly until liver chemistry test abnormalities resolve, stabilise, or return to baseline.

In case of abnormal liver function tests of concurrent measurements of ALT and/or AST $\ge 3 \times \text{ULN}$ with total bilirubin $\ge 2 \times \text{ULN}$ or prothrombin INR $\ge 1.5 \times \text{ULN}$, re-sampling for ALP, ALT, AST, bilirubin, and prothrombin INR should be done immediately, without undue delay and no later than within 24 hours from initial sampling time and the abnormality should be should be reported as an SAE (see Section 10.3.4 for reporting of SAEs). Participants should be monitored twice weekly until liver function test abnormalities resolve, stabilise, or return to baseline.

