Phototoxicity	Refer to alitretinoin product information.	Participants will be instructed to avoid excessive exposure to sunlight or sunlamps and to use sun protection (see Section 5.3.1). The use of tanning bed and phototherapy is forbidden at least 28 days before the first dose and until the end of the trial (see Section 6.8.3).
Psychiatric disorders	Refer to alitretinoin product information.	Patients with psychiatric disorders within the last year or current self-reported depression or mood disturbance will be excluded from the trial (exclusion criterion 11). Mental health will be monitored during the treatment period (see Section 8.2.6) and a specific discontinuation criterion is defined in case of mental health issues (see Section 7.1).
Lipid metabolism	Refer to alitretinoin product information.	Participants with uncontrolled hypercholesterolemia and hypertriglyceridemia will not be enrolled in the trial. (exclusion criteria 6.c and 6.d) Fasting triglycerides and cholesterol parameters will be monitored every 4 weeks during treatment and 2 weeks after the last dose (see Section 8.2.4) and participants with increased lipids that cannot be controlled at an acceptable level are required to discontinue alitretinoin (see Section 7.1).

Potential Risk of Clinical Significance	Summary of Data/Rationale for Risk	Mitigation Strategy
Male fertility	Based on non-clinical findings, the male fertility may be compromised by treatment with alitretinoin. No effects on male or female reproductive parameters were observed at the highest dose tested which reached similar plasma concentrations as those observed in humans. As with other retinoids, reversible effects on male reproductive organs were observed in experimental animals in the form of disturbed spermatogenesis and associated degenerative lesions of the testes. The safety margin in dogs with regard to the no-effect level of toxicity to male reproductive organs was 1-6 for a human dose of 30 mg	If a male is planning to reproduce during the treatment, he should be made aware that his fertility could potentially be reversibly compromised during the treatment period. The information should be given prior to enrolment and stated in the ICF.

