To compare the efficacy and health-related quality of life of twice-daily topical application of delgocitinib cream with once-daily oral administration of alitretinoin capsules in the treatment of patients with severe CHE.	 Efficacy: IGA-CHE TS at Week 24. HECSI-75 at Week 12 and Week 24. HECSI-90 at Week 24. Change in HESD itch score (weekly average) from baseline to Week 24. Reduction of HESD itch score (weekly average) of ≥3 points ¹ at Week 12 and Week 24 AUC from baseline to Week 24 of reduction of HESD 				

Objectives	Endpoints
	itch score (weekly average) of ≥3 points ¹ .
	• Reduction of HESD itch score (weekly average) of ≥4 points ² at Week 12 and Week 24
	• AUC from baseline to Week 24 of reduction of HESD itch score (weekly average) of ≥4 points ² .
	Change in HESD pain score (weekly average) from baseline to Week 24.
	• Reduction of HESD pain score (weekly average) of ≥3 points ³ at Week 12 and Week 24.
	• AUC from baseline to Week 24 of reduction of HESD pain score (weekly average) of ≥3 points ³ .
	• Reduction of HESD pain score (weekly average) of ≥4 points ⁴ at Week 12 and Week 24.
	AUC from baseline to Week 24 of reduction of HESD pain score (weekly average) of ≥4 points ⁴ .
	Change in HESD score (weekly average) from baseline to Week 12 and Week 24.
	 Reduction of HESD score (weekly average) of ≥3 points ⁵ at Week 12 and Week 24.
	 Reduction of HESD score (weekly average) of ≥4 points ⁶ at Week 12 and Week 24.
	Health-related quality of life:
	Change in DLQI score from baseline to Week 12 and Week 24.
	• Reduction of DLQI score of ≥4 points ⁷ at Week 12 and Week 24.
	DLQI score of 0 or 1 at Week 12 and Week 24.
	Change in HEIS (individual domains and total score) from baseline to Week 12 and Week 24.
	Change in EQ-5D-5L index score from baseline to Week 12 and Week 24.
	Change in EQ-5D-5L visual analogue scale score from baseline to Week 12 and Week 24.
To evaluate the effect of twice-daily topical	TSQM at Week 12 and at Week 24.
application of delgocitinib cream on treatment satisfaction and work productivity compared with once-daily oral administration of alitretinoin capsules in the treatment of patients with severe CHE.	Change in WPAI-CHE (each individual domain) score from baseline to Week 12 and Week 24 ⁸ .
To compare the safety of twice-daily topical application of delgocitinib cream with once-daily	• Number of events of increased levels of triglycerides >3.42 mmol/L (fasted state) up to Week 26.

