9.3.11.3 Clinical Laboratory Evaluation

For laboratory parameters, the absolute values as well as the changes from baseline will be summarised by visit for each treatment group.

A shift table will be produced for relevant parameters showing the categories at baseline against those at each post-baseline visit.

For participants with post-baseline values, the number of events reported up to Week 26 will be summarised. For the following laboratory abnormalities endpoints, binary estimand strategy will be applied, as described in Section 9.3.6.3:

- Increased levels of triglycerides >3.42 mmol/L (fasted state).
- Increased levels of cholesterol >7.75 mmol/L (fasted state).
- Increased levels of ALT and/or AST >3×ULN (or >3×baseline if baseline was abnormal but <2×ULN).
- Increased levels of ALP > 2.5 × ULN.
- Increased levels of bilirubin >1.5×ULN up to Week 26.

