10.2 Appendix 2: Clinical Laboratory Tests

The tests detailed in Table 10-1 will be performed by a central laboratory.

Local laboratory results are only required in the event that the central laboratory results are not available in time for either IMP administration and/or response evaluation. If a local sample is required, it is important that the sample for central analysis is obtained at the same time. Additionally, if the local laboratory results are used to make either an IMP decision or response evaluation, the results must be recorded.

Protocol-specific requirements for inclusion or exclusion of participants are detailed in Section 5 of the protocol.

Additional tests may be performed at any time during the trial as determined necessary by the investigator or required by local regulations.

Investigators must document their review of each laboratory safety report.

Table 10-1 Protocol-required Safety Laboratory Tests

Laboratory Tests	Parameters	
Haematology	Thrombocytes	Leukocytes with differential count:
	Erythrocytes	Neutrophils
	Haemoglobin	Lymphocytes
	Haematocrit	Monocytes
	Erythrocyte indices:	Eosinophils
	Erythrocyte mean corpuscular volume (MCV)	Basophils
	Erythrocyte mean corpuscular haemoglobin (MCH)	
	% Reticulocytes	
Clinical chemistry	Urea nitrogen	AST/SGOT ²
	Potassium	Total and direct bilirubin ²
	Creatinine	ALT/SGPT ²
	Sodium	Prothrombin INR ²
	Glucose fasting ¹	Protein
	Calcium	Alkaline phosphatase ³
	Cholesterol (LDL, HDL total) fasting ¹	Gamma glutamyl transferase
	Triglycerides fasting ¹	Lactate dehydrogenase
		Albumin

Laboratory Tests	Parameters
Routine urinalysis	Specific gravity
	Glucose, protein, occult blood, ketones, nitrite, leukocytes by dipstick
	Urine samples will be tested at the trial site (dipstick). It will be at the investigator's discretion to decide whether a urine sample should be sent to the central laboratory for microscopic examination (WBC; RBC; epithelial cells, squamous; epithelial cells, transitional; epithelial cells, renal tubular; hyaline casts; WBC casts; RBC casts; waxy casts; granular casts; calcium oxalate crystals; uric acid crystals; triphosphate crystals; yeast; and bacteria).
Pregnancy testing (WOCBP only)	Highly sensitive urine hCG pregnancy test (as needed for women of childbearing potential) at timepoints detailed in Section 8.3.5. ⁴
Other screening tests	Follicle-stimulating hormone and oestradiol (as needed in women of non-childbearing potential only)

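### If visits go remote, fasting lipids stay on schedule for alitretinoin but become discretionary for delgocitinib, and the exceedance counts in Section 9.3.11.3 make no allowance for it

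*Combined protocol and SAP*

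**What the plan says.** On site, the arms are sampled alike. The fasting lipid row of Table 1-1 names the central laboratory and has no arm restriction. It gives seven post-baseline samples: Weeks 4, 8, 12, 16, 20 and 24, and the follow-up visit. Table 2-1 agrees: "Fasting triglycerides and cholesterol parameters will be monitored every 4 weeks during treatment and 2 weeks after the last dose".

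At remote visits the rule differs by arm. In Appendix 5 (Section 10.5), the list of data to be collected remotely has a sub-list headed "For participants treated with alitretinoin", and its first item is: "Serum cholesterol and serum triglycerides (fasting values) should continue to be monitored by a local laboratory", at the Table 1-1 timepoints. No lipid item exists for delgocitinib. The general rule for periods without on-site visits is: "It will be at the discretion of the investigator to decide whether clinical laboratory samples are considered necessary to ensure participant safety". It adds: "If possible, a home visit can be arranged for a healthcare professional to collect relevant clinical laboratory samples".

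The endpoints are counts. Table 3-2 lists, among the exploratory safety endpoints, "Number of events of increased levels of triglycerides >3.42 mmol/L (fasted state) up to Week 26" and a matching one for cholesterol above 7.75 mmol/L. Section 9.3.11.3 states: "For participants with post-baseline values, the number of events reported up to Week 26 will be summarised". It then sends these endpoints to the binary strategy of Section 9.3.6.3. It does not mention the number of samples, the laboratory used, or remote visits.

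**The concern.** An exceedance can be recorded only when a sample is drawn. If one arm keeps its full schedule through a remote period and the other does not, equal true rates produce unequal recorded counts, and the arm with more samples looks worse. Section 4.2 says the related adverse events were chosen as endpoints because of alitretinoin's known safety profile, so readers will take the lipid results as a tolerability contrast between the products. Part of that contrast could come from the sampling rule.

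Nothing else in the plan repairs this. The COVID-19 provisions in Section 9.3.2 are written for the primary and key secondary endpoints. The event rate per patient-year in Section 9.3.11.1 is for adverse events, and it uses observation time rather than sampled time. The liver endpoints in the same section are not affected in this way, because the remote rule for those tests is the same in both arms.

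**Working it through.** The plan gives no figure on this point, so there is none to reproduce. The calculation isolates ascertainment by giving both arms the same true rate.

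**Inputs**
- Participants per arm: N = 255 (Section 9.5).
- Scheduled post-baseline lipid samples: K = 7 (Table 1-1).
- Share of lipid visits held remotely: f. Not in the documents; assumed 5% to 30%.
- Share of remote delgocitinib visits that are sampled at discretion: g. Not in the documents; 0 and 0.5 are shown.
- Chance that a sample exceeds the threshold: p. Not in the documents; 3% is used for illustration.
- All local alitretinoin values are assumed to enter the endpoint.

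**Event counts**
- Alitretinoin: N × K × p.
- Delgocitinib: N × K × p × q, where q = 1 − f(1 − g).
- Ratio, alitretinoin to delgocitinib: 1/q. It does not depend on p.

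| f | q, g = 0 | ratio | q, g = 0.5 | ratio |
|---|---|---|---|---|
| 5% | 0.950 | 1.05 | 0.975 | 1.03 |
| 10% | 0.900 | 1.11 | 0.950 | 1.05 |
| 20% | 0.800 | 1.25 | 0.900 | 1.11 |
| 30% | 0.700 | 1.43 | 0.850 | 1.18 |

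Example with f = 20%, g = 0, p = 3%: 255 × 7 × 0.03 = 53.5 expected events on alitretinoin, against 53.5 × 0.8 = 42.8 on delgocitinib. With f = 0 or g = 1, q = 1 and the ratio is 1.00.

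**Participants who ever exceed (p = 3%, g = 0)**
- Independent samples: 1 − (1 − p)^7 = 1 − 0.97^7 = 19.2% on alitretinoin, and 1 − (1 − pq)^7 on delgocitinib. At f = 20% the latter is 1 − 0.976^7 = 15.6%.
- Correlated samples: a beta-binomial model with an assumed intraclass correlation of 0.5, the number of delgocitinib samples being binomial (7, q). A lasting elevation is then usually caught at another visit.

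| f | Alitretinoin, independent | Delgocitinib, independent | Alitretinoin, ICC 0.5 | Delgocitinib, ICC 0.5 |
|---|---|---|---|---|
| 5% | 19.2% | 18.3% | 7.5% | 7.4% |
| 10% | 19.2% | 17.4% | 7.5% | 7.3% |
| 20% | 19.2% | 15.6% | 7.5% | 6.9% |
| 30% | 19.2% | 13.8% | 7.5% | 6.5% |

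At f = 20% the gap falls from 3.6 to 0.6 percentage points. The count ratio is not affected by this correlation.

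**Direction of the binary analysis**

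Section 9.3.9 bases exploratory endpoints on the primary, composite estimand. Under that estimand, Table 9-2 codes COVID-related missing binary data as non-response. For a laboratory exceedance that term is undefined. If it means no event, unsampled delgocitinib visits count as clean and the tilt towards delgocitinib stays. If it means failure, as composite strategies read for efficacy, the same visits count against delgocitinib and the sign could reverse.

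**The case against.** A reader might infer that the comparison is biased towards the sponsor's product as it stands. The documents do not support that. The remote rule applies only when local authority measures prevent on-site visits, and Appendix 5 expects sites to secure attendance. The remote share is unknown and may be zero. No passage says that local values are pooled into the endpoint, and both Table 1-1 and Appendix 2 name the central laboratory. If local values stay out, the extra ascertainment largely disappears. On the other side, Appendix 5 does list these lipids among the data collected remotely, so the question is open.

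A reader might also infer that high local values are recorded selectively, because Appendix 2 says "if the local laboratory results are used to make either an IMP decision or response evaluation, the results must be recorded". That rule concerns central results that arrive too late. The Appendix 5 list covers high and low values alike, so selective recording is not shown.

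The size is easily overstated too. Figures with independent samples and no discretionary delgocitinib sampling are upper values. Seven samples is a ceiling, since participants who stop treatment permanently leave the treatment visits, and the Week 12 primary endpoint and nominal Week 24 visits carry no lipid sample.

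The endpoints are exploratory and outside the testing sequence. Section 9.3.6.1 defers analysis of COVID-related missing-data patterns to the SAP, and the eCRF records whether an assessment was remote or not done. That deferral sits in the efficacy estimand section, though, and may not reach laboratory safety endpoints.

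These objections limit the size and certainty of the effect. They do not remove the unequal rule or the absence of any allowance for it in Section 9.3.11.3.

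**Conclusion.** The point stands in conditional form. If remote visits occur, if delgocitinib participants are then sampled less often, and if the local alitretinoin values enter the endpoint, raw exceedance counts tilt towards delgocitinib. The count ratio under equal true rates is 1.05 to 1.43 for an assumed remote share of 5% to 30% with no discretionary sampling, and 1.03 to 1.18 with half of those visits sampled. For ever-exceeded risk the gap is smaller if elevations persist, and the direction of the binary analysis cannot be settled until the coding is stated. The primary and key secondary results are not touched. Because clinically significant laboratory values are reported as adverse events (Section 8.2.4), the counts of hypertriglyceridaemia and hypercholesterolaemia call for the same caution.

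**What to change.** In Section 9.3.11.3 or the SAP, before database lock:

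- Keep the exceedance table on all available data as the safety summary, so that no genuine event is dropped.
- Add a pre-specified between-arm comparison restricted to central-laboratory samples from on-site visits in both arms, and base comparative statements on it.
- Report the number of lipid samples per arm, or exceedances per sample, beside the counts. This also shows differences due to early discontinuation, which the restriction alone does not remove.
- List local-laboratory values separately.
- State that a missing sample is not coded as an exceedance.

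The cost is SAP wording and one extra table, using visit-status data that the eCRF already collects. The downside is slightly fewer events in the comparative analysis. No change to clinical monitoring is proposed.
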